### **9.1.8. Investigator Inspections**

The investigator will make available all source documents and other records for this study to Gilead's appointed study monitors, to IRBs/IECs, or to regulatory authority or health authority inspectors.

### **9.1.9. Protocol Compliance**

The investigator is responsible for ensuring the study is conducted in accordance with the procedures and evaluations described in this protocol.

## **9.2. Sponsor Responsibilities**

### **9.2.1. Protocol Modifications**

Protocol modifications, except those intended to reduce immediate risk to study participants, may be made only by Gilead. The investigator must submit all protocol modifications to the IRB/IEC in accordance with local requirements and receive documented IRB/IEC approval before modifications can be implemented.

## **9.2.2. Study Report and Publications**

A clinical study report will be prepared and provided to the regulatory agency. Gilead will ensure that the report meets the standards set out in the ICH Guideline for Structure and Content of Clinical Study Reports (ICH E3). Note that an abbreviated report may be prepared in certain cases.

Investigators in this study may communicate, orally present, or publish in scientific journals or other scholarly media only after the following conditions have been met:

The results of the study in their entirety have been publicly disclosed by or with the consent of Gilead in an abstract, manuscript, or presentation form or the study has been completed at all study sites for at least 2 years

The investigator will submit to Gilead any proposed publication or presentation along with the respective scientific journal or presentation forum at least 30 days before submission of the publication or presentation.

No such communication, presentation, or publication will include Gilead's confidential information (see Section [9.1.5](#)).

The investigator will comply with Gilead's request to delete references to its confidential information (other than the study results) in any paper or presentation and agrees to withhold publication or presentation for an additional 60 days in order to obtain patent protection if deemed necessary.

## **9.3. Joint Investigator/Sponsor Responsibilities**

### **9.3.1. Payment Reporting**

Investigators and their study staff may be asked to provide services performed under this protocol, eg, attendance at Investigator Meetings. If required under the applicable statutory and regulatory requirements, Gilead will capture and disclose to Federal and State agencies any expenses paid or reimbursed for such services, including any clinical study payments, meal, travel expenses or reimbursements, consulting fees, and any other transfer of value.

### **9.3.2. Access to Information for Monitoring**

The monitor is responsible for routine review of the CRF/eCRF at regular intervals throughout the study to verify adherence to the protocol and the completeness, consistency, and accuracy of the data being entered on them. The monitor should have access to any participant records needed to verify the entries in the CRF/eCRF. The investigator agrees to cooperate with the monitor to ensure that any problems detected through any type of monitoring (central, on site) are resolved.

### **9.3.3. Access to Information for Auditing or Inspections**

Representatives of regulatory authorities or of Gilead may conduct inspections or audits of the clinical study. If the investigator is notified of an inspection by a regulatory authority the investigator agrees to notify the Gilead medical monitor immediately. The investigator agrees to provide to representatives of a regulatory agency or Gilead access to records, facilities, and personnel for the effective conduct of any inspection or audit.

### **9.3.4. Study Discontinuation**

Both Gilead and the investigator reserve the right to terminate the study at any time. Should this be necessary, both parties will arrange discontinuation procedures and notify the participants, appropriate regulatory authority(ies), IRBs, and IECs. In terminating the study, Gilead and the investigator will assure that adequate consideration is given to the protection of the participants' interests.

## 11. APPENDICES

Appendix 1. Investigator Signature Page

Appendix 2. Study Procedures Tablea

Appendix 3. Pregnancy Precautions, Definition for Female of Childbearing Potential, and  
Contraceptive Requirements

**Appendix 2. Study Procedures Tablea**

	Screening	Baseline/ Day 1	Day 2	Day 3	Day 7 (± 1 day)	Day 14 (± 1 day)	Day 28 t Follow-up (± 5 days)
Written Informed Consent	X						
Medical History b	X						
Complete Physical Examination c	X	X				X	
Clinical Symptom Directed Physical Examination d			X	X	X		X
Height	X						
Vital Signs e and Weight	X	X f	X f	X f	X	X	X
Respiratory Status g	X	X	X	X	X	X	X
ALT, AST, Serum Creatinine, and Creatinine Clearance/eGFR h	X						
Chemistry i , Hematology j , and Coagulation k Panels		X		X	X	X	
CCI							
Urine Pregnancy Test m	X						
SARS CoV 2 RT qPCR Testing and Potential Resistance Testing n		X	X	X	X	X	
Documentation of SARS CoV 2 Infection	X						
CCI							
CCI							
Medically Attended Visit Information r		X	X	X	X	X	X
FLU PRO Plus Questionnaire s		X	X	X	X	X	
Study Drug Dosing		X	X	X			
Adverse Events and Concomitant Medications	X	X	X	X	X	X	X

a Study visits may be performed in an outpatient setting, at the participant's home via tele health, virtually or remotely, as permitted by local and institutional regulations. The Day 28 visit may be performed via a phone call.

b Medical history will include the date of first symptoms, overall symptoms, exposure source, demographics, baseline characteristics, allergies and all other medical history.

c A complete physical examination must include source documentation of general appearance and the following body systems: Head, neck, and thyroid; eyes, ears, nose, throat, mouth, and tongue; chest (excluding breasts); respiratory; cardiovascular; lymph nodes, abdomen; skin, hair, nails; musculoskeletal; and neurological. Urogenital and reproductive examination should only be completed if clinically indicated.

- d Clinical symptom directed physical examination will include at least cardiac and respiratory evaluation.
- e Vital signs include heart rate, temperature, and blood pressure.
- f On Days 1, 2 and 3, vital signs to be completed pre infusion, postinfusion, and when postinfusion observation is completed; weight from Screening may be used at Days 1-3.
- g Respiratory status includes respiratory rate and SpO2 on room air.
- h Obtain ALT (and AST where available), serum creatinine, and creatinine clearance/eGFR (calculated using Cockcroft Gault or Schwartz formula; see Section 6.7.2) if not available within 90 days of screening, using a local laboratory.
- i Chemistry: alkaline phosphatase, AST, ALT, total bilirubin, total protein, albumin, lactate dehydrogenase, creatine phosphokinase, bicarbonate, blood urea nitrogen, calcium, chloride, creatinine, glucose, lipase, magnesium, phosphorus, potassium, sodium, uric acid.
- j Hematology: Complete blood count with differential.
- k Coagulation: INR, PT, aPTT  
[REDACTED]
- m Urine pregnancy test will only be done for women of childbearing potential.
- n Nasopharyngeal swab and sputum samples will be collected and stored for SARS CoV 2 RT qPCR and potential resistance testing.  
[REDACTED]  
[REDACTED]
- r Medically attended visit information includes any interactions with health care professionals other than study staff or designees including hospitalization; in person emergency, urgent, or primary care visits; or any other in person visit attended by the participant and a health care profession. Identify the nature and cause of the visit.
- s FLU PRO Plus questionnaire should be completed daily from Day 1 through Day 14 (if available).
- t Only AEs, medically attended visit information, and concomitant medications review are needed if the visit is done by phone.

---

**Appendix 3.      Pregnancy Precautions, Definition for Female of Childbearing Potential, and Contraceptive Requirements**

**1) Definitions**

**a. Definition of Childbearing Potential**

For the purposes of this study, a female born participant is considered of childbearing potential following the initiation of puberty (Tanner stage 2) until becoming post-menopausal, unless permanently sterile or with medically documented ovarian failure. No documentation of Tanner stage will be required for people unless deemed prepubescent.

Women are considered to be in a postmenopausal state when they are  $\geq 54$  years of age with cessation of previously occurring menses for  $\geq 12$  months without an alternative cause.

Permanent sterilization includes hysterectomy, bilateral oophorectomy, or bilateral salpingectomy in a female participant of any age.

**b. Definition of Male Fertility**

For the purposes of this study, a male born participant is considered fertile after the initiation of puberty unless the participant is permanently sterile by bilateral orchidectomy or with medical documentation.

**2) Contraception Requirements for Female Participants**

**a. Study Drug Effects on Pregnancy and Hormonal Contraception**

Data from nonclinical studies of RDV have demonstrated no adverse effect on fertility or embryo-fetal development. Remdesivir has not yet been studied in pregnant women. Before enrolling into studies with RDV, women of childbearing potential must have pregnancy testing performed at screening.

Available data indicate that RDV potentially causes an interaction with hormonal contraception that is considered of limited significance. Hormonal methods must be used with a barrier method.

**b. Contraception Requirements for Female Participants of Childbearing Potential**

The inclusion of non-pregnant female participants of childbearing potential requires the use at least an acceptable contraceptive measure. Female participants must agree to 1 of the following from screening until 30 days after the last study drug dose:

- Complete abstinence from intercourse of reproductive potential. Abstinence is an acceptable method of contraception only when it is in line with the participant's preferred and usual lifestyle.

Or

- Consistent and correct use of 1 of the following methods of birth control listed below:

Non-hormonal intrauterine device (IUD)

Hormonal IUD (must be used in conjunction with a barrier method)

Bilateral tubal occlusion (upon medical assessment of surgical success)

Vasectomy in the male partner (upon medical assessment of surgical success)

Or

- Female participants who wish to use a hormonally-based method must use it in conjunction with a barrier method, preferably a male condom. Hormonal methods are restricted to those associated with the inhibition of ovulation. Hormonally-based contraceptives and barrier methods permitted for use in this protocol are as follows:

Hormonal methods (each method must be used with a barrier method, preferably male condom)

- Oral contraceptives (either combined or progesterone only)
- Injectable progesterone
- Subdermal contraceptive implant
- Transdermal contraceptive patch
- Contraceptive vaginal ring

Barrier methods

- Male condom (with or without spermicide)
- Female condom (with or without spermicide)
- Diaphragm with spermicide
- Cervical cap with spermicide
- Sponge with spermicide

Inclusion of methods of contraception in this list of permitted methods does not imply that the method is approved in any country or region. Methods should only be used if locally approved.

Female participants must also refrain from egg donation and in vitro fertilization during treatment and until the end of contraception requirement.

### **3) Contraception Requirements for Male Participants**

During the study male participants with female partners of childbearing potential should use condoms when engaging in intercourse of reproductive potential.

### **4) Unacceptable Birth Control Methods**

Birth control methods that are unacceptable include periodic abstinence (eg, calendar, ovulation, symptothermal, post-ovulation methods), withdrawal (coitus interruptus), spermicides only, and lactational amenorrhea method. A female condom and a male condom should not be used together.

### **5) Procedures to be Followed in the Event of Pregnancy**

Participants will be instructed to notify the investigator if they become pregnant at any time during the study, or if they become pregnant within 30 days of last study drug dose. Participants who become pregnant or who suspect that they are pregnant during the study must report the information to the investigator. Participants whose partner has become pregnant or suspects she is pregnant during the study must report the information to the investigator. Instructions for reporting pregnancy, partner pregnancy, and pregnancy outcome are outlined in Section [7.7.2.1](#).

## LIST OF ABBREVIATIONS

AE	adverse event
ALT	alanine aminotransferase
AST	aspartate aminotransferase
BLQ	below the limit of quantitation
BMI	body mass index
CI	confidence interval
CMH	Cochran-Mantel-Haenszel
CoV	coronavirus
COVID-19	coronavirus disease 2019
CRF	case report form
CSR	clinical study report
DAIDS	Division of AIDS
DAVG	Time-weighted average change from baseline
DMC	data monitoring committee
ED	Emergency department
ET	early termination
FAS	Full Analysis Set
FLU-PRO®	InFLUenza Patient-Reported Outcome
Hb	Hemoglobin
HLT	high-level term
HLGT	high-level group term
ICH	International Conference on Harmonization (of Technical Requirements for Registration of Pharmaceuticals for Human Use)
IV	Intravenous
IXRS	interactive voice or web response system
LLT	lower-level term
LOD	Limit of detection
LOQ	limit of quantitation
MedDRA	Medical Dictionary for Regulatory Activities
PCR	polymerase chain reaction
CCI	[REDACTED]
PT	preferred term
PTM	Placebo to match
Q1, Q3	first quartile, third quartile
RDV	remdesivir (GS-5734™)
SAE	serious adverse event
SAP	statistical analysis plan
SARS	severe acute respiratory syndrome
SD	standard deviation

SI (units)	international system of units
SOC	system organ class
SpO 2	oxygen saturation
TEAE	treatment-emergent adverse event
TFLs	tables, figures, and listings
ULN	upper limit of normal
WHO	World Health Organization

CCI

## 1. INTRODUCTION

This statistical analysis plan (SAP) describes the statistical analysis methods and data presentations to be used in tables, figures, and listings (TFLs) in the clinical study report (CSR) for Study GS-US-540-9012. This SAP is based on the study protocol amendment 4 dated 14 January 2021 and the electronic case report form (eCRF). The SAP will be finalized before database finalization. Any changes made after the finalization of the SAP will be documented in the CSR.

### 1.1. Study Objectives

The primary objectives of this study are as follows:

- To evaluate the efficacy of RDV in reducing the rate of COVID-19 related hospitalization or all-cause death in non-hospitalized participants with early stage COVID-19
- To evaluate the safety of RDV administered in an outpatient setting

The secondary objectives of this study are as follows:

- To evaluate the efficacy of RDV in reducing the rate of COVID-19 related medically attended visits (MAVs; medical visits attended in person by the participant and a health care professional) or all-cause death in non-hospitalized participants with early stage COVID-19
- To determine the antiviral activity of RDV on SARS-CoV-2 viral load
- To assess the impact of RDV on symptom duration and severity

CCI

A large rectangular area of the page is completely blacked out, representing redacted content. The text 'CCI' is printed in red at the top left corner of this redacted area.

## 1.2. Study Design

This is a Phase 3, randomized, double-blind, placebo-controlled, multicenter study of RDV therapy for outpatients with early stage COVID-19 who are at higher risk of disease progression.

Participants who meet all eligibility criteria may be randomized in a 1:1 ratio to RDV or placebo. Randomization will be stratified by participants who reside in a skilled nursing facility, by participant's age (< 60 vs  $\geq$ 60 years), and by region (United States [US] vs. ex-US):

**Treatment Group A:** single dose of IV RDV 200 mg on Day 1 followed by IV RDV 100 mg on Days 2 and 3 (RDV group)

**Treatment Group B:** IV placebo-to-match (PTM) RDV on Days 1 to 3 (PTM group)

Participants must meet all of the following inclusion criteria to be eligible for participation in this study:

- 1) Willing and able to provide written informed consent (participants  $\geq$  18 years of age) or assent (participants  $\geq$  12 and < 18 years of age) prior to performing study procedures. Participants aged  $\geq$  18 years may be enrolled with the consent of a legal representative where permitted according to local law and approved nationally and by the relevant institutional review board (IRB) or independent ethics committee (IEC). For participants  $\geq$  12 and < 18 years of age, a parent or legal guardian must be willing and able to provide written informed consent prior to performing study procedures
- 2) Either:
  - Age  $\geq$  18 years (at all sites) or aged  $\geq$  12 and < 18 years of age weighing  $\geq$  40 kg (where permitted according to local law and approved nationally and by the relevant IRB or IEC) with at least 1 of the following pre-existing risk factors for progression to hospitalization:
    - a) Chronic lung disease: chronic obstructive pulmonary disease, moderate-to-severe asthma, cystic fibrosis, pulmonary fibrosis
    - b) Hypertension: systemic or pulmonary
    - c) Cardiovascular or cerebrovascular disease: coronary artery disease, congenital heart disease, heart failure, cardiomyopathy, history of stroke, atrial fibrillation, hyperlipidemia
    - d) Diabetes mellitus: Type 1, type 2, or gestational
    - e) Obesity (BMI  $\geq$  30)

- f) Immunocompromised state; having a solid organ transplant, blood, or bone marrow transplant; immune deficiencies; HIV with a low CD4 cell count or not on HIV treatment; prolonged use of corticosteroids; or use of other immune weakening medicines
- g) Chronic mild or moderate kidney disease
- h) Chronic liver disease
- i) Current cancer
- j) Sickle cell disease

— OR age  $\geq$  60 years, regardless of the presence of other pre-existing risk factors for progression

- 3) SARS-CoV-2 infection confirmed by molecular diagnostics (nucleic acid [eg, PCR] or antigen testing)  $\leq$  4 days prior to screening
- 4) Presence of  $\geq$  1 symptom(s) consistent with COVID-19 for  $\leq$  7 days prior to randomization (such as fever, cough, fatigue, shortness of breath, sore throat, headache, myalgia/arthralgia)
- 5) Not currently receiving, requiring, or expected to require supplemental oxygen
- 6) Not currently requiring hospitalization (hospitalization defined as  $\geq$  24 hours of acute care)
- 7) Participants of childbearing potential who engage in heterosexual intercourse must agree to use protocol-specified method(s) of contraception

[figure not shown]
Exclusion criteria for participation include:

- 1) Participation in any other clinical trial of an experimental treatment and prevention for COVID-19
- 2) Prior hospitalization for COVID-19 (hospitalization defined as  $\geq$  24 hours of acute care)
- 3) Treatment with other agents with actual or possible direct antiviral activity against SARS-CoV-2 or administration of any SARS-CoV-2 (or COVID-19) vaccine
- 4) Criterion removed
- 5) Requiring oxygen supplementation
- 6) ALT or AST  $\geq 5 \times$  upper limit of normal (ULN) at screening or within 90 days of screening  
*Note: if per local practice only ALT is routinely measured, exclusion criteria will be evaluated on ALT alone*

- 7) Creatinine clearance < 30 mL/min at screening or within 90 days of screening using the Cockcroft-Gault formula in participants  $\geq$  18 years of age or estimated glomerular filtration rate (eGFR) < 30 mL/min/1.73m^2 at screening or within 90 days of screening using the Schwartz formula in participants < 18 years of age (see Section 6.7.2 of protocol)
- 8) Currently breastfeeding (nursing)
- 9) Known hypersensitivity to the study drug, metabolites, or formulation excipient
- 10) Use or planned use of exclusionary medications (refer to Section 5.4 of protocol)

Participants will receive study treatment with RDV for 3 days (Treatment Group A) or PTM for 3 days (Treatment Group B).

**Figure 1-1. Study Schema**

On study Days 1 through 3, vital signs including respiratory status and SpO2 will be measured, and adverse events (AEs) and concomitant medications will be documented. Laboratory tests for safety (hematology, coagulation and chemistry) will be performed on Days 1, 3, 7, and 14. Nasopharyngeal swabs and sputum samples will be collected on Days 1, 2, 3, 7, and 14 for SARS-CoV-2 quantitative reverse transcriptase polymerase chain reaction viral load testing and possible resistance testing.

On study Day 14 physical examination findings, vital signs including temperature, respiratory rate, and SpO2, AEs and concomitant medications will be documented.

Symptom severity will be assessed daily from Day 1 through Day 14 using the COVID-19 adapted FLU-PRO Plus questionnaire (if available). On study Day 28, there will be an in-person or phone visit. Physical examination, vital signs including temperature, respiratory rate, and SpO2, AEs, MAV information and concomitant medications will be documented (only AEs, MAV information and concomitant medications needed if performed by phone).

CCI

### 1.3. Sample Size and Power

The total sample size of the study will be approximately 1264 participants.

The sample size computation is based on proportions of COVID-19 related hospitalization or all-cause death by Day 28 for the RDV and placebo treatment groups. The sample size needed for a 1:1 randomization using a 2-tailed test at level  $\alpha$  is given by:

$$\frac{(z_{1-\alpha/2} + z_{1-\beta})^2}{P(1 - R^2)\sigma^2 B^2}$$

Where  $P$  is the overall rate of COVID-19 related hospitalization or all-cause death,  $B$  is the log hazard ratio,  $\sigma$  is the standard deviation of treatment indicator variable,  $R$  is the R-Squared that is obtained when treatment indicator variable is regressed on the other covariates, and  $z_{1-\alpha/2}$  and  $z_{1-\beta}$  are the 1- $\alpha/2$  and 1- $\beta$  quantiles of the standard normal distribution.

A sample size of 1264 participants (632 in each group with 1:1 randomization) achieves  $> 90\%$  power to detect a ratio of 0.55 (RDV to placebo) in proportion of COVID-19 related hospitalization or all-cause death, which is equal to a hazard ratio of 0.534) using a two-sided significance level of 0.05 assuming the overall COVID-19 related hospitalization or all-cause death rate is 9.3% (12% in the placebo group and 6.6% in the RDV group) and a 5% drop out rate. The sample size provides approximately 80% power to detect a smaller treatment effect size with a ratio of 0.60 (RDV to placebo), assuming a 2-sided significance level of 0.05 and the overall COVID-19 related hospitalization or all-cause death rate is 9.6% (12% in the placebo group and 7.2% in the RDV group) and a 5% drop out rate. The proportion of patients with COVID-19-related hospitalizations or emergency department (ED) visits was 13.5% in high risk patients (age  $\geq 65$  or BMI  $\geq 35$ ) who received placebo {[Gottlieb 2021](#)}, 12% is assumed for the study to account for decrease in hospitalization rate in recent months.

The sample size calculation was done using software PASS (Version 14.0, module of Cox regression for survival).

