#### **2.1.1. DMC Analysis**

One external multidisciplinary DMC was planned to review the progress of the study and to perform interim reviews of the efficacy (futility assessment) and safety data. However, this DMC analysis was not performed due to the stop of study enrollment after 584 participants randomized and prior to reaching the planned DMC analysis schedule (ie, approximately 50% of the total 1264 planned participants have completed Day 28 assessment).

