### **2.3. Changes from Protocol-Specified Analyses**

The DMC analysis was not performed due to the stop of enrollment on 08 April 2021 after less than 50% of the participants were randomized. The reasons of stopping enrollment were due to significant changes in the epidemiology of COVID-19 from a combination of lower hospitalization rates and high vaccine rates in high-risk patients, and a change in the unmet patient need for convenient at home options for non-hospitalized patients with COIVD-19. The decision to stop study enrollment was documented on 06-APR-2021 Study Management Team meeting minutes.

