##### **3.1.2. Full Analysis Set**

The primary analysis set for efficacy analysis is defined as the Full Analysis Set (FAS), which will include all participants who (1) are randomized into the study, and (2) have received at least 1 dose of study treatment. Participants will be grouped according to the treatment to which they were randomized.

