### **3.5. Multiple Comparisons**

There will be no multiplicity adjustment in the final analysis. Efficacy will be evaluated using the primary efficacy endpoint at the significance level of 0.05. All other efficacy endpoints are exploratory in nature and will be tested using 2-sided tests at the 5% significance level without multiplicity adjustment.

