#### 6.1.3. Primary Analysis of the Primary Efficacy Endpoint

The hazard ratio of COVID-19 related hospitalization or all-cause death between the two treatment groups will be estimated using a Cox model with stratification factors as covariates.

If a participant prematurely discontinues from the study prior to Day 28 or the hospitalization status is missing, the participant is censored at last study date or day 28 whichever is earlier. If a participant has a COVID-19 related hospitalization first and then dies, then date of the COVID-19 related hospitalization and status will be used for the primary analysis for this participant. If a participant has a non COVID-19 related hospitalization first and then dies without experiencing a COVID-19 related hospitalization, then date of the death and status will be used for the primary analysis for this participant.

The hazard ratio, p-value, 95% CI for the hazard ratio from Cox model, and proportion of COVID-19 related hospitalization or all-cause death at Day 28 from Kaplan-Meier estimate will be provided.

The FAS will be the primary analysis set for efficacy endpoint evaluation. The primary endpoint may be analyzed for each of the subgroups defined in Section 3.3.

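### SAP 1.3 still gives 1264 participants and over 90% power as the study's size and power, although the SAP records a stop at 584, where its own formula gives about 61%

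*SAP*

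**What the plan says.** SAP 1.3 opens with "The total sample size of the study will be approximately 1264 participants". It then gives the Cox-regression sample size formula and two power statements for 632 per group at a two-sided 0.05 level with 5% dropout:

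- more than 90% power for a ratio of 0.55 (12% vs 6.6%, hazard ratio 0.534);
- about 80% power for a ratio of 0.60 (12% vs 7.2%).

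The placebo rate was already set below a cited 13.5%: "12% is assumed for the study to account for decrease in hospitalization rate in recent months".

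SAP 2.1.1 explains that the DMC analysis was not done "due to the stop of study enrollment after 584 participants randomized and prior to reaching the planned DMC analysis schedule". SAP 2.3 dates this as a "stop of enrollment on 08 April 2021 after less than 50% of the participants were randomized" and gives among the reasons "significant changes in the epidemiology of COVID-19 from a combination of lower hospitalization rates and high vaccine rates in high-risk patients".

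The primary test is unchanged. SAP 3.5 says "Efficacy will be evaluated using the primary efficacy endpoint at the significance level of 0.05", and SAP 6.1.3 will report "The hazard ratio, p-value, 95% CI for the hazard ratio from Cox model". The Full Analysis Set (SAP 3.1.2) takes participants who "are randomized into the study, and (2) have received at least 1 dose of study treatment".

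**The concern.** The SAP was brought up to date for the enrollment stop in 2.1.1 and 2.3 but not in 1.3. Section 1.3 does not say that 1264 is the original target, does not mention the stop and does not refer the reader forward. Section 2.3 lists only the dropped DMC analysis as a change, and 6.4 only the changed test for oxygen supplementation. No visible section gives power, expected events or precision for the trial as enrolled.

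The primary endpoint keeps a test at 0.05, and the only visible power figures beside it belong to a trial more than twice the size. A reader of a non-significant result who goes to 1.3 would take the chance of missing a ratio of 0.55 to be under 10%. Under the plan's own assumptions at 584 it is close to 40%.

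**Working it through.** **Inputs**

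- From SAP 1.3: N = 1264; two-sided alpha 0.05; 1:1 allocation, so the variance of the treatment indicator is 0.25; dropout 5%; event rates 12% vs 6.6% (overall P = 9.3%) and 12% vs 7.2% (overall P = 9.6%).
- From SAP 2.1.1: 584 randomized. 584/1264 = 46.2%.
- Assumed: R-squared of treatment on the other covariates = 0. The SAP gives no value. Zero is natural under randomization, and the effect of a larger value is bounded below.

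**Formulas**

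- HR = ln(1 − p_RDV) / ln(1 − p_placebo)
- Expected events = N × 0.95 × P
- The SAP's formula solved for power: Φ( √(events × 0.25 × (1 − R²)) × |ln HR| − 1.96 )

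**Hazard ratios**

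- Ratio 0.55: ln(0.934)/ln(0.88) = 0.534, as the SAP states; |ln HR| = 0.627.
- Ratio 0.60: ln(0.928)/ln(0.88) = 0.585; |ln HR| = 0.537.

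**The plan's own figures, N = 1264**

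- Ratio 0.55: 1264 × 0.95 × 0.093 = 111.7 events; √(111.7 × 0.25) × 0.627 − 1.96 = 1.35; power 91.2%. This agrees with the stated figure of over 90%.
- Ratio 0.60: 1264 × 0.95 × 0.096 = 115.3 events; √(115.3 × 0.25) × 0.537 − 1.96 = 0.92; power 82.2%. This is about 2 points above the stated 80%, which the SAP gives as approximate.

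**The trial as enrolled, N = 584**

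- Ratio 0.55: 584 × 0.95 × 0.093 = 51.6 events; √(51.6 × 0.25) × 0.627 − 1.96 = 0.29; power 61.5%.
- Ratio 0.60: 584 × 0.95 × 0.096 = 53.3 events; √(53.3 × 0.25) × 0.537 − 1.96 ≈ 0; power 50.0%.

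**Effect of the unstated R-squared.** With 5% dropout, power above 90% at 1264 requires R-squared below 0.043. At that limit, power at 584 is 59.6% (ratio 0.55) and 48.3% (ratio 0.60). Within the SAP's formula and dropout rate, the ranges are therefore 59.6% to 61.5% and 48.3% to 50.0%.

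**Effect of the method (ratio 0.55, N = 584).** Omitting the dropout deduction gives 63.7%. With 5% dropout, Freedman's formula gives 58.8%, a comparison of two proportions 59.1%, and using the ratio itself as the hazard ratio 57.4%.

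**Detectable effect at 584 (12% placebo rate, 5% dropout, R-squared 0).** Power of 80% needs a ratio of about 0.46 (HR 0.448), and 90% needs about 0.40 (HR 0.387).

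**Effect of a lower placebo rate at 584.** The rates below 12% are assumptions, since the documents give none.

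| Placebo rate | Power, ratio 0.55 | Power, ratio 0.60 |
|---|---|---|
| 12% | 61.5% | 50.0% |
| 10% | 53.1% | 42.6% |
| 8% | 44.0% | 34.9% |
| 6% | 34.2% | 27.1% |
| 5% | 29.2% | 23.2% |

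**The case against.** The best defence is that 1.3 is a design statement. It ties the power to a sample of 1264, and that conditional statement remains true. The section repeats protocol 8.9 almost unchanged, adding only the basis for the 12% rate. The SAP also keeps the protocol's future tense elsewhere, for example for randomization. The next section but one, 2.1.1, calls 1264 planned and gives 584, and 2.3 gives the date and reasons, so only someone reading 1.3 in isolation would be misled. Once enrollment is fixed, the confidence interval carries the precision, and restating power is arguably optional.

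Much of this stands. The 1264 calculation is not wrong, nothing is hidden, and the planned interval will show what was achieved. It does not remove the inconsistency: the opening sentence of 1.3 states a size that the same document shows will not be reached, and disclosing the stop does not state what it does to power. Nor is this observed power computed after the fact. The effect, event rates and formula are the pre-specified ones, and only N changes.

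Two technical cautions are fair. The range of 59.6% to 61.5% belongs to one formula with the 5% dropout deducted. Discontinued participants are censored and so contribute some follow-up, and across the methods tried the spread is about 57% to 64%. The dropout deduction is nevertheless the SAP's own assumption. Second, the lower hospitalization rates cited in 2.3 need not carry over fully to this placebo arm, because vaccinated people were excluded and 1.3 had already lowered 13.5% to 12%. A lower rate is therefore a possibility, not a finding.

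**Conclusion.** The concern holds, at minor severity. The size given in SAP 1.3, and the power resting on it, do not describe the trial that was enrolled. For a ratio of 0.55, power falls from 91.2% at 1264 to 61.5% at 584; for 0.60, it falls from 82.2% to 50.0%. Expected events fall from about 112 to 52 and from about 115 to 53.

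These figures rest on the SAP's formula, a 12% placebo rate, 5% dropout and R-squared of 0. They also take all 584 randomized participants as the starting number. The Full Analysis Set requires at least one dose, so the analysed number may be smaller. Type I error is not affected.

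**What to change.** In SAP 1.3, label the 1264 calculation as the original planned design, cross-refer to 2.1.1, and add text such as:

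> Enrollment stopped after 584 participants were randomized. Under the original assumptions (5% dropout; R-squared taken as 0) this gives about 52 expected events and about 61% power for a ratio of 0.55, and about 53 events and 50% power for a ratio of 0.60; the number in the FAS may be smaller. Power would be lower still if the placebo rate is below 12%.

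In SAP 2.3, list the reduced sample size of 584 and its power alongside the enrollment stop. The label and cross-reference remove the inconsistency; the added figures tell the reader its consequence.

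The cost is a few sentences of SAP wording and a less favourable stated power, with no change to any analysis and no extra patients.
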